3.2. Selection of Doses

3.2.1. Experimental Treatments

This study will enroll subjects into cohorts as outlined in Section 3.1.2.

In this study, a range of single, IV doses will be evaluated during the dose escalation. The starting dose of 0.6 mg (loading dose of 0.15 mg as 0.5-hour IV infusion, followed by a maintenance dose of 0.45 mg as 5.5-hour IV infusion), was selected based on safety, PK, and PD data from a healthy volunteer (including elderly subjects) study (DS1040-A-U101).

Based on human PK data, the projected maximum (peak) observed concentration in circulating blood (C_{max}) and area under the plasma concentration-time curve (AUC) of the 0.6 mg starting dose in a typical subject with a body weight of 75 kg and a creatinine clearance of 90 mL/min are: 13.2 ng/mL and 118 ng·h/mL, respectively, which are 1.2% and 1.5% of the highest exposure achieved in healthy young subjects (mean C_{max} = 1102 ng/mL in the 12 mg 0.5-hour IV infusion dose level and mean area under the concentration-versus-time curve from time 0 extrapolated to infinity [AUC_{inf}] = 8116 ng·h/mL in the 40 mg 24-hour IV infusion dose level), and 2.6% and 10.4% of the highest exposure achieved in elderly subjects (mean C_{max} = 505 ng/mL and mean AUC_{inf} = 1135 ng·h/mL in the 6 mg 0.5-hour IV infusion dose level). Projected plasma exposure levels for planned doses are summarized in Table 3.2. Based on human biomarker data, the projected PK exposure at the starting dose of 0.6 mg will likely result in an approximately 15% reduction in clot lysis time.

The maximum dose of 9.6 mg (loading dose of 2.4 mg as 0.5-hour IV infusion, followed by maintenance dose of 7.2 mg as 5.5-hour IV infusion) was selected to achieve full effect on clot lysis time reduction. Projected C_{max} and AUC_{inf} are 212 ng/mL and 1889 ng·h/mL, respectively, which are 19% and 23% of the highest exposure achieved in healthy, young subjects, and 42% and 166% of the highest exposure achieved in elderly subjects.

Table 3.2: Projected Plasma Pharmacokinetic Parameters

Cohort	Total Dose (mg)	Loading Dose (mg) over 0.5 hours	Maintenance Dose (mg) over 5.5 hours	Simulated Plasma PK Parameters			
				C _{0.5h} (ng/mL)	C _{6h} (C _{max}) (ng/mL)	t _{max} (h)	AUC (ng·h/mL)
1	0.6	0.15	0.45	11.9	13.2	6	118
2	1.2	0.3	0.9	23.8	26.5	6	236
3	2.4	0.6	1.8	47.7	52.9	6	472
4	4.8	1.2	3.6	95.3	106	6	944
5	9.6	2.4	7.2	191	212	6	1889

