
6.1.7. 12 Hours Postdose

The following assessments will be performed 12 hours after dosing:

- Obtain supine vital sign measurements
- Perform a 12-lead ECG in triplicate
- Obtain blood samples for PT, INR, aPTT, and fibrinogen (Section 9.5)
- Obtain PD blood sample (TAFIa activity, clot lysis, D-dimer) (Section 8.2)
- Obtain PK blood sample

6.2. Day 2

The following assessments will be performed on Day 2 (24 hours after dosing):

- Obtain supine vital sign measurements
- Record prior/concomitant medication
- Perform a 12-lead ECG in triplicate
- Obtain blood samples for safety laboratory assessments (serum chemistry and hematology) (Section 9.5)
- Obtain a urine sample for urinalysis (Section 9.5)
- Obtain blood samples for PT, INR, aPTT, and fibrinogen (Section 9.5)
- Obtain PD blood sample (TAFIa activity, clot lysis, TAFI antigen, D-dimer) (Section 8.2)
- Perform a CT or MR angiography
- Administer the NIHSS
- Assess subjects for adverse events
- Obtain PK blood sample

Collection of urine for urine PK should stop 24 hours after dosing.

Subjects can be discharged at any time after 24 hours following dosing, at the discretion of the Principal Investigator. In the case of discharge prior to Day 5, after completing early discharge procedures (described in Section 6.5), no further assessments are required until the Day 30 Follow-up Visit.

6.3. Day 3

The following assessments will be performed on Day 3 (48 hours after dosing):

- Obtain supine vital sign measurements
- Record prior/concomitant medication
- Obtain blood samples for safety laboratory assessments (serum chemistry and hematology) (Section 9.5)

- Obtain a urine sample for urinalysis (Section 9.5)
- Obtain blood samples for PT, INR, aPTT, and fibrinogen (Section 9.5)
- Obtain PD blood sample (TAFIa activity, clot lysis, D-dimer) (Section 8.2)
- Assess subjects for adverse events
- Obtain PK blood sample

6.4. Day 4

The following activities and/or assessments will be performed on Day 4 (72 hours after dosing):

- Record prior/concomitant medication
- Assess subjects for adverse events
- Obtain PK blood sample

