8.1. Pharmacokinetic (PK) Variable(s)

Blood samples for PK assessment will be collected predose and 0.5, 3, 6, 9, 12, 24, 48, 72, and 96 hours postdose. The PK parameters that will be calculated from the plasma concentrations of DS-1040a using noncompartmental analysis are shown in Table 8.1.

Table 8.1: Pharmacokinetic Parameters - Plasma

Parameter	Definition
AUC_{last} (ng·h/mL)	The area under the concentration-versus-time curve, from time 0 to the last quantifiable concentration sampling point
C_{max} (ng/mL)	Maximum (peak) observed plasma concentration
t_{max} (h)	The time of maximum observed concentration

If data permit, the following parameters will be estimated: the area under the concentration-versus-time curve, from time 0 extrapolated to infinity (AUC_{0-inf}), $t_{1/2}$, clearance, and the volume of distribution in the terminal elimination phase.

Urine collection for PK assessment will start following dosing and stop at 24 hours postdose. The PK parameters that will be calculated from the urine concentration of DS-1040b are shown in Table 8.2.

Table 8.2: Pharmacokinetic Parameters - Urine

Parameter	Definition
Ae_{0-24}	Cumulative amount of compound excreted into urine up to 24 hours
CL_R	Renal clearance
$\%Fe_{0-24}$	Cumulative percentage of dose excreted into urine up to 24 hours

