11.5. Pharmacokinetic/Pharmacodynamic Analyses

11.5.1. Pharmacokinetic Analyses

Descriptive statistics (sample size [N], number missing [N missing], arithmetic mean, SD, %CV, minimum, maximum, and median) of DS-1040a plasma concentrations at each sampling time point and all PK parameters, including urinary PK will be presented by dose. In addition, the geometric mean and %CV for geometric mean will also be calculated for the PK parameters AUC_{0-inf} , AUC_{last} , and C_{max} .

Mean and median plasma concentration versus time data will be presented graphically for all treatments using original and semi-log scales.

Actual sampling times that differ from the scheduled sampling times by more than 5 minutes within the first hour, or by more than 30 minutes within the first 12 hours, or by more than 1 hour thereafter, will be listed but excluded from summary statistics at each timepoint and mean and median graphs.

The relationship between dose and exposure parameters (AUC_{0-inf} , AUC_{last} , and C_{max}) will be examined graphically.

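### Section 11.5.1 gives no slope or interval for exposure against dose, and AUClast, which has no common end time, is the weakest of its three measures for that comparison

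*Combined protocol and SAP*

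**What the plan says.** Section 11.5.1 names three exposure measures, AUC0-inf, AUClast and Cmax. On "The relationship between dose and exposure parameters" its whole method is that it "will be examined graphically". It gives no slope, dose-normalised comparison, interval or criterion. The same section does plan numerical summaries of every PK parameter by dose, and adds that "the geometric mean and %CV for geometric mean will also be calculated for the PK parameters" named above.

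Section 8.1 (Table 8.1) defines AUClast as running "from time 0 to the last quantifiable concentration sampling point". AUC0-inf is conditional: "If data permit, the following parameters will be estimated". No AUC over a fixed interval is listed. Plasma is sampled before dosing and at 0.5, 3, 6, 9, 12, 24, 48, 72 and 96 h. For urine, "Urine collection for PK assessment will start following dosing and stop at 24 hours postdose". Table 8.2 lists Ae0-24 and renal clearance (CLR) but gives no formula for CLR.

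Section 6.2 states that "Subjects can be discharged at any time after 24 hours following dosing". The early-discharge procedures in Section 6.5 include one PK sample, and nothing more is then required until Day 30. The opening of Section 8 also allows PK samples to be changed or dropped after a dose-escalation review.

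On the projections, Section 3.2.1 says "Projected plasma exposure levels for planned doses are summarized in Table 3.2". They assume 75 kg and a creatinine clearance of 90 mL/min.

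**The concern.** Plasma PK is the first-listed secondary objective, and the five planned doses cover a 16-fold range on projections that scale exactly with dose. Proportional exposure has been reported in healthy subjects (Section 1.1.1.5). This is the first study in stroke patients, and whether the scaling carries over is a natural question for its PK data. A plot can suggest an answer, but it does not say how large a departure the data rule out.

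The choice of measure adds a second difficulty. AUClast stops where concentrations fall below the assay limit, which happens sooner at low doses. Low doses then lose a larger share of their true AUC, so AUClast can look more than proportional when exposure is in fact proportional. A plot of AUClast would not separate the two explanations.

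**Working it through.** **1. Table 3.2 reproduced.** AUC/dose is 118/0.6 = 196.7 at the lowest dose and 1889/9.6 = 196.8 at the highest. Cmax/dose is 22.0 to 22.1 and C0.5h/dose is 19.8 to 19.9. Log-log slopes are 1.000 (AUC), 1.001 (Cmax) and 1.001 (C0.5h), so the table is proportional apart from rounding. The stated percentages of healthy-subject exposure also reproduce, for example 13.2/1102 = 1.2% and 1889/1135 = 166%.

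**2. Precision of a power model.** The model is ln(exposure) = a + b ln(dose), with SE(b) = σ/√Sxx and σ = √ln(1+CV²). Active numbers come from Table 3.1: 6, 6, 12, 12, 12 (48 in all), or 12 per dose (60). With dose coded 0 to 4 in doublings:
- 48 active: mean 114/48 = 2.375; Sxx = (354 − 48 × 2.375²) × (ln 2)² = 83.25 × 0.4805 = 40.0.
- 60 active: Sxx = 120 × 0.4805 = 57.7.

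The between-subject CV is not in the documents, so a range is assumed. At CV 30%, σ = 0.294 and SE = 0.294/√40.0 = 0.046. The 90% half-width is 1.679 × 0.046 = 0.078, and 16^0.078 = 1.24.

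| Assumed CV | 48 active: half-width (factor over 16-fold) | 60 active |
|---|---|---|
| 20% | 0.053 (1.16) | 0.044 (1.13) |
| 30% | 0.078 (1.24) | 0.065 (1.20) |
| 50% | 0.125 (1.42) | 0.104 (1.33) |

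**3. Truncation of AUClast, simple version.** From Table 3.2 at 0.6 mg, AUC0-6 ≈ ½ × 0.5 × 11.9 + ½ × (11.9 + 13.2) × 5.5 = 3 + 69 = 72, which leaves 118 − 72 = 46 after 6 h. A single exponential then has time constant 46/13.2 = 3.5 h. If the last quantifiable sample were at 12 h (assumed), the missing area is 13.2 × exp(−6/3.5) × 3.5 = 8.3, or 7% of 118. Stopping at 24 h loses 13.2 × exp(−18/3.5) × 3.5 = 0.27, about 0.2%. With 12 h at 0.6 mg and 24 h at 9.6 mg, the captured fractions differ by 0.998/0.930 = 1.07.

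**4. Truncation with a slower tail.** A two-exponential curve was matched to C0.5h, C6h and AUC in Table 3.2, with the terminal half-life set at 3 to 24 h (the 3 h case matches only approximately). AUClast was cut at the last scheduled sample at or above an assay limit of 0.1 to 2 ng/mL. Both ranges are assumptions.
- Example, half-life 12 h and limit 1 ng/mL: the last quantifiable samples are at 12, 24, 24, 48 and 48 h for the five doses. The captured shares are 83.6, 92.0, 92.0, 98.0 and 98.0%. The ratio of highest to lowest dose is 98.0/83.6 = 1.17 and the apparent slope is 1.055.
- Over the whole grid the apparent slope is 1.00 to 1.08 and the ratio 1.00 to 1.25, under exact proportionality.

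**5. Discharge.** Stopping at 24 h loses about 1% of AUC at half-lives of 3 to 3.5 h and 12% at 24 h. The documents show no link between discharge time and dose.

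**6. Cmax.** It is projected at 6 h, before any discharge, and its lowest value of 13.2 ng/mL is well above every assay limit tried.

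**7. Does a 24 h cut alone cure it?** No. In the example above, the 24 h sample at 0.6 mg is itself below the limit. If the area still ends at the last quantifiable sample, the ratio only falls from 1.17 to 92.0/83.6 = 1.10. A rule for such values is needed as well.

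**The case against.** The strongest reply is that the information is already there. N, geometric mean and geometric %CV by dose for all three measures let anyone regress log geometric means on log dose, weighting by N, and obtain the slope; the pooled log variances give its standard error. Proportionality is not a named objective, Section 11.2 makes all analyses descriptive and hypothesis-generating, and escalation follows the safety review and bleeding rules, not a PK test. Section 11 also defers detailed methods to an analysis plan, which might add a regression. These points stand, and they keep the matter small. They do not remove it: Section 11.5.1 already names its method, a plot, and Section 8.1 already fixes the parameter list.

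A reader might infer that the trial cannot say whether exposure is proportional. The documents do not support that, because the by-dose summaries, an unaffected Cmax and a conditional AUC0-inf are all planned. A reader might also infer that early discharge distorts the dose comparison. It does not do so materially. The loss is about 0.2% in the simple calculation, larger losses need an assumed slow tail, an early-discharge PK sample is taken, and nothing ties discharge to dose.

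The assay-limit effect is also conditional, since neither the limit nor the terminal half-life is given.

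**Conclusion.** The concern holds as a minor analysis gap. What is missing is a prespecified estimate with an interval, and an AUC over a common time. The slope could be known to about ±0.04 to ±0.13 (90% CI) for CVs of 20 to 50%. The possible artefact in AUClast, up to 0.08 on the slope, is about as large as the half-width at CV 30% with 48 subjects. It may equally be nil if the assay is sensitive. CV, assay limit and half-life are all assumptions.

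The added slope should not be read as a proof of proportionality. If an assumed 0.80 to 1.25 limit were applied over the 16-fold range, b would have to lie within 1 ± ln(1.25)/ln(16), or 0.92 to 1.08. When b is truly 1, the chance that the 90% CI fits inside is 63 to 84% at CV 20%, 8 to 32% at CV 30% and about nil at CV 50% (48 to 60 active). The slope also speaks only to scaling; a higher level of exposure at every dose would show in the geometric means already planned.

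**What to change.** Keep the plots and make these additions.

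- **Section 11.5.1:** a descriptive power model, log(exposure) = a + b log(dose), with b and its 90% CI for Cmax, AUC0-24 and, where estimable, AUC0-inf. State that this is estimation, with no acceptance limit. Continue to summarise AUClast, but do not use it for the slope.
- **Table 8.1:** AUC0-24, with a written rule for concentrations below the assay limit up to and including 24 h. The 24 h sample is already scheduled, and subjects stay in hospital for at least 24 h, so no new sample is needed. If PK sampling is changed under Section 8, that sample should be retained in every cohort.
- **Table 8.2:** define CLR as Ae0-24/AUC0-24, so that the urine and plasma intervals match.

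The cost is one regression, one more noncompartmental parameter and a short handling rule. No extra subjects, visits or blood are required.

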11.5.2. Pharmacodynamic Analyses

Raw values for total TAFIa activity, clot lysis time, D-dimer will be presented graphically by subject, and will also be summarized by time point and treatment. Change from baseline values (absolute value and percentage) will also be summarized. Pooled placebo data of all cohorts will be summarized.

Recanalization will be assessed using TIMI reperfusion criteria. Raw values of reperfusion score will be presented graphically by subject, and will also be summarized by treatment. Change from baseline values will be summarized. The shift (baseline to posttreatment) of the number and percentage of subjects in TIMI reperfusion criteria will be tabulated by treatment. Pooled placebo data of all cohorts will be summarized.

11.5.3. Biomarker and Exploratory Analyses

Exploratory PGx analyses for the potential predictive benefits of DS-1040b may be assessed later in a separate report.

11.6. Safety Analyses

Safety parameters will include SAE, TEAEs, physical examination findings, vital signs measurements, standard clinical laboratory parameters (serum chemistry, hematology, urinalysis, and coagulation parameters), and ECG parameters.

Safety analyses in general will be descriptive and will be presented in tabular format with the appropriate summary statistics.

Values for safety assessments will be summarized by treatment group. Results from placebo-treated subjects will be pooled across cohorts.

11.6.1. Adverse Event Analyses

Results from placebo subjects will be pooled across cohorts.

A TEAE is defined as an adverse event that: emerges during the treatment period (from first dose date until 30 days after the last dosing date), having been absent at predose; or reemerges during treatment, having been present at baseline but stopped prior to treatment; or worsens in severity after starting treatment relative to the predose state, when the adverse event is continuous.

Adverse events will be coded using Medical Dictionary for Regulatory Activities (MedDRA) and will be summarized and listed by treatment, System Organ Class (SOC), and preferred term.

The number and percentage of subjects reporting TEAEs will be tabulated by SOC and preferred term.

Similarly, the number and percentage of subjects reporting treatment emergent SAEs will be tabulated, as well as TEAEs/SAEs considered related to DS-1040b.

A by subject adverse event (including TEAEs) data listing including, but not limited to, verbatim term, preferred term, SOC, and relationship to study drug will be provided.

Deaths, other SAEs, and other significant adverse events, including those leading to permanent discontinuation from DS-1040b, will be listed.

11.6.2. Clinical Laboratory Evaluation Analyses

Descriptive statistics by treatment will be provided for the clinical laboratory test results (hematology, serum chemistry, urinalysis, and coagulation) and changes from baseline by scheduled time of evaluation. Percentage change from baseline will also be summarized for coagulation variables. Clinical laboratory values will be summarized by treatment and listed with abnormal values flagged.

Abnormal laboratory results will be evaluated. A shift table (in categories of low, normal and high, when appropriate) will be provided for selected clinical laboratory tests.

Abnormal clinical laboratory test results deemed of clinical significance will be listed.

Data for PT, INR, and aPTT will be summarized with descriptive statistics by treatment.

11.6.3. Vital Sign Analyses

Descriptive statistics will be provided for the vital signs measurements and changes from baseline by scheduled time of evaluation. Vital signs will be summarized by treatment and listed with abnormal values flagged.

11.6.4. Electrocardiogram Analyses

Electrocardiogram parameters (PR, RR, QRS, QT, corrected QT interval using Bazett's formula [QTcB], and corrected QT intervals using Fridericia's formula [QTcF]) will be summarized by treatment using descriptive statistics for actual values and for changes from baseline by scheduled time of evaluation. The corrected QT intervals using Bazett's and Fridericia's formula will be calculated as follows: $QTcB = QT/(RR)^{1/2}$ and $QTcF = QT/(RR)^{1/3}$.

The incidence of notable ECG changes in maximum absolute QT, QTcF and QTcB intervals (> 450 , > 480 , and > 500 ms) over all postdose evaluations, as well as in QT, QTcF and QTcB maximum changes from baseline (> 30 and > 60 ms) over all postdose evaluations will be summarized. A listing of ECG data will be provided.

Electrocardiogram values will be summarized by treatment and listed with abnormal values flagged.

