6.1.1. Predose

The following assessments will be performed predose:

- Obtain written (ie, signed and dated) informed consent
- Assess inclusion/exclusion criteria
- Record medical history information (including mRS, if possible)
- Record prior/concomitant medication
- Obtain a blood sample for follicle stimulating hormone evaluation
- Obtain a serum sample for pregnancy testing in women of childbearing potential (childbearing potential is assumed in women up to 55 years of age)
- Perform a complete physical examination including weight (can be estimated by the subject, family members, or the Principal Investigator)
- Perform a non-contrast CT or MR, followed by angiography (after hemorrhagic stroke is ruled out)
- Administer the NIHSS
- Obtain supine vital sign measurements
- Perform a 12-lead ECG in triplicate
- Obtain blood samples for safety laboratory assessments (serum chemistry and hematology) (Section 9.5)
- Obtain a urine sample for urinalysis (Section 9.5)
- Obtain blood samples for PT, INR, aPTT, and fibrinogen (Section 9.5)
- Obtain PD blood sample (TAFIa activity, clot lysis, TAFI antigen, D-dimer) (Section 8.2)
- Assess subjects for adverse events
- Obtain PK blood sample

6.1.2. 0 Hour

The following assessments will be performed at 0 hour:

- Administer DS-1040b
- Start collection of urine for PK assessments

An optional PGx sample can be obtained at any time after dosing.

6.1.3. 0.5 Hours Postdose

The following assessments will be performed 0.5 hours after dosing started:

- Obtain supine vital sign measurements
- Perform a 12-lead ECG in triplicate
- Obtain blood samples for PT, INR, aPTT, and fibrinogen (Section 9.5)
- Obtain PD blood sample (TAFIa activity, clot lysis, D-dimer) (Section 8.2)
- Obtain PK blood sample

6.1.4. 3 Hours Postdose

The following assessments will be performed 3 hours after dosing:

- Obtain supine vital sign measurements
- Perform a 12-lead ECG in triplicate
- Obtain PK blood sample

6.1.5. 6 Hours Postdose

The following assessments will be performed 6 hours after dosing:

- Obtain supine vital sign measurements
- Perform a 12-lead ECG in triplicate
- Obtain blood samples for PT, INR, aPTT, and fibrinogen (Section 9.5)
- Obtain PD blood sample (TAFIa activity, clot lysis, TAFI antigen, D-dimer) (Section 8.2)
- Administer the NIHSS
- Assess subjects for adverse events
- Obtain PK blood sample

6.1.6. 9 Hours Postdose

The following assessment will be performed 9 hours after dosing:

- Obtain PK blood sample

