9.7. Electrocardiograms

Standard supine 12-lead ECGs will be performed by qualified technicians in triplicate on the ECG machine dedicated to this study. Electrocardiograms will be reviewed at the site for treatment of any urgent issues. The clinical significance of any ECG change must be assessed by the Investigator in the context of the subject's medical history, physical examination, and concomitant medications. The Investigator or delegated physician will review, sign, and date all ECGs.

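### Section 11.6.4 counts subjects already above a QT threshold before dosing as having a notable ECG change, and applies its outlier cut-offs to uncorrected QT

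*Combined protocol and SAP*

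**What the plan says.** Section 11.6.4 defines two sets of outlier counts. The first is "The incidence of notable ECG changes in maximum absolute QT, QTcF and QTcB intervals", with cut-offs of 450, 480 and 500 ms applied to each subject's highest postdose value. The second covers "maximum changes from baseline (> 30 and > 60 ms) over all postdose evaluations", again for QT, QTcF and QTcB. Nothing in the section makes the absolute counts depend on the predose value.

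The same section gives the corrections: QTcB = QT/RR^(1/2) and QTcF = QT/RR^(1/3). It also plans descriptive summaries of PR, RR, QRS, QT, QTcB and QTcF, both actual values and changes, by scheduled time, and a listing with abnormal values flagged.

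Section 9.7 states: "Standard supine 12-lead ECGs will be performed by qualified technicians in triplicate". Sections 6.1 and 6.2 place these ECGs predose and at 0.5, 3, 6, 12 and 24 hours. No section says how the three tracings at a time point are combined. Section 11 leaves detailed methods to an analysis plan to be finalised before database lock; the documents contain no further ECG analysis text.

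None of the inclusion or exclusion criteria in Sections 4.1.1 and 4.1.2 names QT or QTc. Only the general investigator-discretion criterion could keep out a subject with a long baseline interval.

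**The concern.** A table of notable changes should count something that changed after dosing. The absolute counts do not: a subject at 455 ms throughout is counted above 450 ms, and so is a subject who rose from 420 to 455 ms. The table cannot tell them apart.

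Uncorrected QT shortens as heart rate rises and lengthens as it falls. A fixed cut-off on raw QT, or on its change, therefore partly measures heart rate.

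Safety is the primary objective, and Table 3.1 gives 6 or 12 active subjects per dose in Cohorts 1 and 2 and 12 in Cohorts 3 to 5. In arms of that size, one or two subjects with a long predose QTc, or with a marked change in heart rate, can shape how a by-dose row reads.

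**Working it through.** The plan states no QT rate, mean or SD, so there is no figure to reproduce. The uncorrected-QT point follows exactly from the plan's formula. The baseline point can be sized only under assumptions.

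**1. Uncorrected QT.** With RR = 60/HR in seconds, the protocol's formula gives QT = QTcF × (60/HR)^(1/3). The heart rates and QTcF values below are examples, not document values.

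- QTcF constant at 410 ms. At 85 bpm, QT = 410 × 0.8904 = 365.1 ms. At 65 bpm, QT = 410 × 0.9737 = 399.2 ms. The rise is 34.1 ms, which passes the 30 ms change cut-off although QTcF has not moved.
- The QTcF at which QT reaches 450 ms is 450/(60/HR)^(1/3). At 50 bpm it is 450/1.0627 = 423.5 ms. At 100 bpm it is 450/0.8434 = 533.5 ms.

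The raw-QT count can therefore flag an unremarkable QTcF at a slow rate and miss a long one at a fast rate.

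Bazett's formula errs with rate too, in the other direction. QTcF 430 ms at 90 bpm corresponds to QT 375.6 ms and QTcB 460.1 ms. Hence QTcB serves better as support than as the main count.

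**2. No predose condition.** Assumptions, none from the documents: mean QTc 415 to 440 ms, between-subject SD 20 to 25 ms, visit-to-visit SD 0 to 10 ms, tracing SD 5 to 15 ms, normal distributions, no drug effect. Triplicates are averaged and there are five postdose times.

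The SD of a triplicate mean around a subject's own level is s = √(visit SD² + tracing SD²/3). For a subject with true level b:

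- p(b) = 1 − Φ((450 − b)/s) is the chance that one triplicate mean exceeds 450 ms.
- 1 − (1 − p(b))^5 is the chance that the maximum of five postdose means exceeds it.
- The proportion counted is the second quantity averaged over b. The proportion counted and already above 450 ms predose is the average of the product of the two.

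| Mean | Between-subject SD | Visit SD | Tracing SD | s | Counted > 450 ms | Of these, already > 450 ms predose | Newly > 450 ms |
|---|---|---|---|---|---|---|---|
| 415 | 20 | 0 | 5 | 2.9 | 5.8% | 69% | 1.8% |
| 415 | 20 | 5 | 5 | 5.8 | 8.2% | 51% | 4.0% |
| 415 | 20 | 10 | 15 | 13.2 | 18.5% | 31% | 12.8% |
| 430 | 20 | 5 | 5 | 5.8 | 25.7% | 62% | 9.8% |
| 430 | 20 | 10 | 10 | 11.5 | 37.9% | 45% | 20.7% |
| 440 | 25 | 0 | 5 | 2.9 | 39.6% | 86% | 5.5% |
| 440 | 20 | 10 | 15 | 13.2 | 59.6% | 53% | 28.3% |

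A simulation of 200,000 subjects per setting agrees to within rounding and Monte Carlo error. Across the grid, about 6% to 60% are counted (roughly 1 to 7 of 12), and about 31% to 86% of those were above 450 ms before dosing. The higher cut-offs are much less affected: on the same grid, at most about 18% exceed 480 ms and 5% exceed 500 ms.

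**3. What is not affected.** A QTcF change above 30 or 60 ms is measured from the subject's own baseline and is rate-corrected. Neither problem reaches it.

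**The case against.** The strongest reply is that most of what is needed is already planned. True change categories stand beside the absolute ones. QTcF has its own counts, which raw QT does not contaminate. RR is summarised. Section 11.2 gives predose, postdose and change summaries with pooled placebo, and the listing lets a reader pick out subjects who were long at baseline. This stands, and it limits the consequence. It does not make the absolute counts measure change, and pooled placebo does not remove chance predose imbalance in arms of 6 to 12.

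A second objection is that counting only new exceedances has a price. A subject going from 455 to 479 ms would enter no row: excluded at 450, below 480, and with a change of 24 ms. This is correct, and it is why the new counts should stand beside the all-subject counts and not replace them.

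Two stronger readings are tempting, and the documents do not support them.

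- A reader might infer that the maximum is taken over 15 single postdose tracings (5 times × 3) without averaging. The plan is silent on this. Its summaries are by scheduled time, which fits one value per time at least as well, and the detail may belong to the deferred analysis plan.
- A reader might infer that escalation decisions are at risk. The prespecified rules in Section 3.1.6 concern symptomatic intracranial haemorrhage and major bleeding, with discretionary halting for other reasons. The escalation review in Section 11.9 names clinical adverse-event data and safety laboratory data.

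**Conclusion.** The point holds on two counts, both visible in the wording of Section 11.6.4: the absolute thresholds include subjects already above them at predose, and both the absolute and the change cut-offs are applied to uncorrected QT.

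The heart-rate effect is exact for the examples given. The size of the baseline effect is not known. The ranges in the working depend wholly on assumed means and SDs and on averaged triplicates, and show only that the share of pre-existing cases at 450 ms could be substantial. No distorted dose trend has been demonstrated.

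The impact is confined to descriptive safety tables, which Section 11.2 calls exploratory and hypothesis-generating. How the triplicates are combined is a detail to clarify, not an error found. The change is worth making because the tables serve the primary objective and the repair is small.

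**What to change.** In Section 11.6.4 or the analysis plan that details it:

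1. For each of 450, 480 and 500 ms, report by treatment the number of subjects newly above the threshold (predose at or below it), with the number at risk as denominator, beside the all-subject count. A shift table of predose category against maximum postdose category would do the same. Section 11.6.2 already plans shift tables for selected laboratory tests.
2. Limit the outlier and change counts to QTcF, with QTcB as supportive. Keep uncorrected QT in the descriptive summaries and the listing.
3. State, as a clarification, that the mean of the three tracings at each time, predose included, is the analysis value from which baselines, changes and maxima are derived.

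The cost is a few sentences and revised table shells, settled before database lock. No data collection changes, and because the all-subject counts and the listing remain, no subject drops out of view.
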